#### A Randomized Controlled Trial of Ultrasonic Aspiration versus CO2 Laser Ablation for the Treatment of Vulvar Intraepithelial Neoplasia

#### 1. Introduction

Vulvar intraepithelial neoplasia (VIN) is a chronic precancerous medical condition causing vulvar dysplasia affecting nearly 50,000 women in the United States each year. [1]The causes of pre-cancer of the vulva are multi-factorial but common risk factors including multiple sexual partners, early age at first coitus, smoking, and a history of vulvar irritation. Common to all of these causes is the association with the infection by the HPV virus. While the HPV vaccine has been used extensively to control the development of pre-cancer of the cervix, the effectiveness of this treatment has not been shown in pre-cancer of the vulva. Additionally, pre-cancers of the vulvar generally affect women in the 4th and 5th decade of life and therefore, many women have not received the HPV vaccine. If untreated, pre-cancers of the vulva can further develop into invasive cancers. The treatment of an actual vulvar cancer can include radical surgery for removal of the vulva, extensive dissection of the groins to obtain lymph nodes, as well as chemotherapy and radiation. These treatments can be incredible disfiguring, painful, and can have significant side effects for women.

Incidence of VIN is increasing among women and there still lacks a standard of care for optimal treatment. Current treatment options aim to treat the symptoms associated with VIN and result in a high recurrence rate. Repeated treatment leads to psychosocial and sexual distress and decreased guality of life for the affected women.[1] Treatment for vulvar dysplasia usually occurs in 3 categories: surgical excision, laser ablation and topical treatment with immune modulators. While the efficacy of all three modalities has been shown, each one has the potential for side effects. Surgical excision is difficult in multimodal disease states as this can leave the vulvar significantly disfigured. CO2 laser ablation, while effective, has been documented to scar and cause significant pain in the 1-2 weeks following surgery. [2] Topical treatments with imiguimod (an immune modulator) take up to 16 weeks to work, are difficult to apply and can cause local site irritation. Due to the high reoccurrence rate and the nature of the current treatments, a more effective treatment option is warranted. An effective treatment that targets only the diseased areas could potentially decrease recurrence rates. Additionally, a more conservative treatment modality could contribute to reduced risks of scarring, discomfort, and psychosocial and sexual distraught.

Currently there are no recent studies that have compared ultrasonic laser aspiration with conventional treatment methods. Von Greunigen et al compared CO2 laser ablation in women with VIN with ultrasonic aspiration in a randomized trial from 2000-2005. This study found no difference in recurrence rates between the two techniques (HR=.96, 95% CI .64-1.50) and suggested that women who underwent ultrasonic aspiration had less pain and less disfigurement as compared to women who underwent CO2 laser ablation. While this study is compelling, due

to its age and statistical flaws, ultrasonic aspiration has yet to be accepted as a major modality by which to treat VIN. [3]

## 1.1 Significance

Vulva preserving treatments are necessary women with dysplasia in order to maintain function and decrease discomfort typical with a vulvectomy. [4] However, these less invasive techniques have a high recurrence rate. Recurrence is particularly greater for those with HPV and multifocal disease. [5, 6] Women must follow these treatments with long-term surveillance, which often leads to repeat treatment and eventually dysfunction and psychological morbidity. [5] Studies have found that recurrence rates with CO2 laser ablation can range from 25-50% recurrence, while rates for ultrasonic aspiration have been found to range from 22-35% recurrence. [5, 7-13] [2, 14]

Von Greugenigen's study failed to limit the study to women with high-grade dysplasia only. As a result, the final analysis failed to meet statistical power. No RCT has been conducted since looking at reoccurrence difference and QOL outcomes associated with ultrasonic aspiration vs. CO2 laser.[3]

We propose a similar study by which to randomize women to either CO2 laser ablation or ultrasonic aspiration for the treatment of vulvar dysplasia. We estimate that we need 150 patients to achieve statistical power. We will similarly evaluate patients at 3, 6 and 12 months to assess for recurrence and pain. We will also have patients complete quality of life (QOL) surveys to assess which differences in wellness and function following treatment at baseline, 6, and 12 months.

# 2. Study Objectives

The primary objective of this study is to evaluate the incidence of vulva dysplasia recurrence within 12 months of treatment with CO2 laser ablation or ultrasonic aspiration. Women referred for treatment following diagnosis of VIN II/III will be randomized to receive CO2 laser ablation (typical treatment for these cases) or ultrasonic aspiration (approved treatment providing a more targeted technique).

Secondary objectives will examine incidences of pain, scarring, and sexual and psychosocial distraught following treatment for high-grade dysplasia.

# 2.1 Hypothesis

- Hypothesis 1: Treatment for VIN II/III with ultrasonic aspiration will have a 60% reduction in recurrence rates over 12 months as compared to CO2 laser aspiration.
- Hypothesis 2: Treatment for VIN II/III with ultrasonic aspiration will demonstrate decreased incidence of pain and scarring up to 6 weeks following treatment as compared to CO2 laser aspiration.

Hypothesis 3: Treatment for VIN II/III with ultrasonic aspiration will demonstrate a decrease in change of sexual and psychosocial function (as demonstrated with validated instruments) in the 12 months following treatment as compared to CO2 laser aspiration.

### 3. Preliminary Studies and Research Centers

#### 3.1 Principal Investigator and Research Center

#### 4. Outcome Measures

Primary Outcome: The primary outcome of this study is recurrence rates of dysplasia within 12 months of treatment. Rates of recurrence will be compared for CO2 laser ablation and ultrasonic aspiration, stratifying groups based on HPV and multifocal disease status. Recurrence will be assessed at 3, 6, and 12 months following treatment. Recurrence will be determined by repeat visual exam and colposcopy (followed by biopsy as warranted) at each of the follow-up visits. Those with recurrence will be discontinued from the study and receive appropriate treatment for their recurring dysplasia, per standard of care (SOC).

#### Secondary outcomes:

Secondary outcomes will compare:

1) Incidence of pain in the initial 7-10 days following treatment. Pain will be assessed using a patient pain scale. Participants will be asked to assess their own pain and report to the research team.

2) Incidence of scarring due to treatment regimen. Participants will be examined during regular post-procedure visit approximately 4-6 weeks following treatment. A visual exam of the vulva will be conducted to assess scaring.

3) Sexual function will be measured at baseline and at the 6 and 12 month follow-up visits. Changes in sexual function will be compared to baseline within each treatment arm. Overall sexual dysfunction rates will be compared between treatment arms for each study time interval. The Female Sexual Function (FSFI) and the Female Sexual Distraught Survey will be used to examine sexual function at each time point.

4) Wellness and Function will be measured using a validated instrument FACT-V health survey, designed specifically for women with vulva disease. The FACT-V provides metrics for functional, emotional, physical, and social well-being. Wellness and function scores will be compared between treatment arms for each study time interval and compared to baseline within each treatment arm.

Demographic and clinical data will also be collected in order to describe the study population and determine differences among the randomized groups. Demographic and clinical data will be verified against the participant medical records to assure data completion and minimize missing data in our analysis.

Demographic data will include: name, medical record number, contact information, date of birth, age, race/ethnicity, relationship status, and smoking status. Identifying information (name, medical record number, and contact information) will not be entered into the database by ancillary sites, and will only be used by research site to verify data, access medical records, and contact the patient for study visits. At these sites, a log will be kept with their identifiable data and participants will be linked to their study chart by study ID.

Clinical Data will include: menopause status, colposcopy results, treatment history, history of STDs, pre-existing medical conditions, concomitant medications, allergies, and vitals (blood pressure, pulse, temperature, respiratory rate, height, weight, BMI).

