# 6. Investigational Plan

## 6.1 Description of Population to be Enrolled

Women diagnosed with high-grade vulvar intraepithelial neoplasia (VIN II/III) will be eligible to participate. Women with prior treatment for dysplasia will be considered eligible for the study. Prior treatment for dysplasia includes all treatments such as surgery, laser ablation, and/or aldara (a topical agent).

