Surveys	Pain Assessment	Scar Assessment	Vitals (inc. height/weight)	Physical Exam	(biopsy if needed)	assessment/colposcopy	Adverse Events	Procedures	Medications and	Concomitant	Medical History	Randomization	criteria)	(Inclusion/Exclusion	Confirm eligibility	Informed Consent	Procedures		
×			×	×	×		×	×			×		×			×		Baseline visit	V0: Screening
			×		×		×	×				×						0-30 days following V0	V1: Enrollment
	×																	7-10 days after treatment (survey only)	V2: Pain Assessment
	×	×	×		×		×	×										4-6 weeks after treatment	V3: Scarring Assessment
×	×		×	×	×		×	×										6 months following treatment	V4: 6 month follow up (±30 days)
×	×		×	×	×		×	×										12 months following treatment	V5: 12 month follow up (±30 days)
Ultr CON	× asoi IIRI	nic A 8 # 1	× Aspira 6-070	× tion 1	× vs.	C02	× Lase	× r A	bla	tio	n Vo	ersio	on	04,	/12	/20			Unanticipated Visit

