- Presence of scarring (~30% of women receiving CO2 laser, less than 5% in women receiving ultrasonic aspirator)
- Dysureia or burning (~25% of women)
- Adhesions (less than 5%)
- Infection: yeast, UTI, or other (~10% of women)
- Abnormal discharge (less than 10% of women)
- Eschar (~10% of women). [1]

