## 14.2 Secondary Endpoints

The secondary endpoints for this study are as follows:

Pain: Pain in the initial 7-10 days following treatment will be self-assessed using a pain scale. Average pain scores and incidence of high-level of pain will be determined for each treatment arm.

Scarring: Scarring in the 6 weeks following treatment will be assessed via visual exam by a study investigator. Incidence rates of scarring will be determined for each treatment arm.

Sexual function and sexual distraught: Sexual function and distraught will be assessed at baseline, 6, and 12 months following treatment. Mean scores for

function and distraught will be determined for each treatment arm per study time-point. Sexual function and distraught will be measured with validated instruments, The Female Sexual Function Index, and the Female Sexual Distress survey (Appendix 1.3 and 1.4).

Wellness and Function: General wellness and function will be assessed at baseline, 6, and 12 months following treatment. Mean scores for general function will be determined for each treatment arm per study time-point. Wellness will be measured using the validated instrument FACTS survey for vulvar malignancies (Appendix 1.2).

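### Treatment-related scarring is examined once, at 4-6 weeks, with no recorded pre-treatment scar status, although previously treated women are eligible, so old scars can be counted as new ones in either arm

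*Combined protocol and SAP*

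**What the plan says.** Section 4 (Secondary outcomes) names the outcome as "Incidence of scarring due to treatment regimen". On timing and method it says "Participants will be examined during regular post-procedure visit approximately 4-6 weeks following treatment" and "A visual exam of the vulva will be conducted to assess scaring". Section 14.2 adds "Scarring in the 6 weeks following treatment will be assessed via visual exam by a study investigator" and "Incidence rates of scarring will be determined for each treatment arm". Hypothesis 2 in section 2.1 predicts a lower incidence with aspiration up to 6 weeks.

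The table in the Study Calendar is broken in the text available, but its column order can be read. Scar assessment is marked in one row only, "V3: Scarring Assessment". The V0 row carries surveys, vitals, physical exam and colposcopy. The V1 row (treatment visit) carries vitals and colposcopy. Section 4.1 describes baseline as surveys plus demographic and clinical data. The clinical data listed in section 4 include treatment history and colposcopy results, but not scar status.

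Section 6.1 states "Women with prior treatment for dysplasia will be considered eligible for the study" and counts surgery, laser ablation and a topical agent as prior treatment. Section 6.1.2 has no exclusion for existing scars. Section 1 reports that laser can scar, and section 11.1 expects scarring in about 30% of women after laser and in fewer than 5% after the aspirator.

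Section 14 compares scarring between arms by chi-square, with no baseline term. Randomisation is stratified by multifocal disease and HPV status, not by prior treatment (section 6.3). The only person stated to be blinded is the statistician (section 7.1).

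**The concern.** An incidence attributed to the study procedure needs a known state before the procedure. Sexual function and the FACT-V scores have a baseline in this plan; scarring does not. By the protocol's own account, a woman who has had laser before may arrive with a scar. At V3 the examiner must decide whether a visible scar is old or new. The plan gives no scale, no attribution rule and no pre-treatment scar record to help.

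Scarring is half of Hypothesis 2, and less scarring is one of the main advantages put forward for aspiration. If old scars enter the count, neither arm's rate can be read as caused by treatment and the difference between arms shrinks. A pre-treatment status that was never recorded cannot be collected once treatment has been given.

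**Working it through.** **The plan's own figures.** The documents give no power or sample size for scarring. The 62 evaluable and 75 enrolled per arm in section 6.2 are for recurrence (37.5% v 15%, 80% power). The usual two-sided formula gives 59 per arm uncorrected and 68 with continuity correction, and power at 62 is 82%. So 62 lies between standard variants. It is used below only as a number of women, and the point does not depend on it.

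**Inputs.**
- New-scar rates: laser p = 0.30, aspirator p = 0.05 (section 11.1; the aspirator figure is stated as an upper limit).
- n = 62 and n = 75 per arm (section 6.2).
- s, the share scarred at entry: not in the documents, so assumed. If 25%, 50% or 75% of women were previously treated and 30% of those carry a scar, s = 0.30 × 0.25 = 7.5%, 0.30 × 0.50 = 15%, or 0.30 × 0.75 = 22.5%.
- f, the share of old scars counted as new: not in the documents. f = 1 is the worst case; f = 0.5 is shown beside it.

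**Formulas.** Recorded rate in an arm = fs + (1 − fs)p. The difference between arms is (1 − fs)(0.30 − 0.05), so it shrinks by the factor 1 − fs. With p₁ and p₂ the recorded rates and p̄ their mean, two-sided chi-square power at 0.05 (normal approximation) is

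Φ{ [ |p₁ − p₂| − 1.96 √(2p̄(1 − p̄)/n) ] / √([p₁(1 − p₁) + p₂(1 − p₂)]/n) }.

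**Worked case, s = 15%, f = 1, n = 62.** p₁ = 0.15 + 0.85 × 0.30 = 0.405; p₂ = 0.15 + 0.85 × 0.05 = 0.1925; difference 0.2125; p̄ = 0.29875. The null standard error is √(2 × 0.29875 × 0.70125/62) = 0.0822, and the alternative standard error is √((0.2410 + 0.1554)/62) = 0.0800. Power = Φ[(0.2125 − 1.96 × 0.0822)/0.0800] = Φ(0.64) = 74%.

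**All old scars counted (f = 1).**

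| Scarred at entry | Recorded rates, laser v aspirator | Difference (points) | Risk ratio | Power, 62 per arm | Power, 75 per arm |
|---|---|---|---|---|---|
| 0% | 30% v 5% | 25.0 | 6.0 | 96% | 99% |
| 7.5% | 35% v 12% | 23.1 | 2.9 | 87% | 92% |
| 15% | 41% v 19% | 21.3 | 2.1 | 74% | 82% |
| 22.5% | 46% v 26% | 19.4 | 1.7 | 62% | 70% |

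**Half of old scars counted (f = 0.5).** The effective shares are 3.75%, 7.5% and 11.25%. Power at 62 per arm is 92%, 87% and 80%.

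**The case against.** The strongest reply is that both the outcome's name and section 14.2 ask for scarring that follows from the study treatment, so the examiner is expected to leave old scars out. Some information for doing so exists. There is a physical exam at V0, colposcopy at V0 and V1, and a treatment history checked against medical records, and the examiners are experienced gynaecologists (section 7.1). The case report form is not shown, and it may ask whether a scar is new. This much stands: a reader might infer that every old scar will be recorded as incident, or that nothing is known about the vulva before treatment, and the documents support neither. What remains is that no scar finding is required before treatment and no rule says how to attribute one, so the separation rests on individual judgement.

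The illustration also leans towards the worst case. It applies the laser scarring figure to every prior treatment, including a topical agent for which section 1 mentions only local irritation. It also assumes the scars are still visible at entry. And 62 per arm is net of losses over 12 months, whereas scarring is read at 4-6 weeks, so 75 may be nearer. These points are fair, and the half-counted and 75-per-arm figures are given for that reason.

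A reader might also infer that old scars bias the comparison towards one device, or that a chance imbalance in them raises the false-positive rate. Neither follows. Old scars precede randomisation, so they are balanced in expectation, and their sampling variation is already in the chi-square standard error. Dilution works against the hypothesised benefit of aspiration. Unblinded attribution could in principle favour an arm, but nothing in the documents shows that it would.

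**Conclusion.** The point holds as a gap in how a secondary outcome is measured. The plan claims treatment-caused incidence but records no pre-treatment scar status in a population that may already be scarred. The consequence is that old scars can be counted in either arm, which inflates both rates and dilutes the contrast.

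The size is uncertain. If few women arrive scarred, or most old scars are recognised, the loss is small (power 92% against 96% at 62 per arm, with 7.5% scarred and half of those counted). If 22.5% arrive scarred and all are counted, power falls to 62% (70% at 75 per arm). These figures rest on the protocol's 30% v 5% and on assumed values for prior scarring and misattribution. The primary endpoint is unaffected. The change is worth making because the remedy is cheap and the missing record cannot be recovered later.

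**What to change.** - **Study Calendar and section 8:** add a scar assessment at V0, or at V1 before treatment, during the examination already done there. Record the presence and location of any scar on the same form to be used at V3. V0 has the advantage that assignment has not yet been drawn, since section 7.1 randomises on the day of surgery.
- **Sections 4 and 14.2:** define the outcome as a scar at V3 that is not on the pre-treatment record.
- **Section 14:** compare arms on that outcome, with baseline scar (yes/no) as a covariate.

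If new scars can be told apart from old ones in this way, the contrast returns to the 0% row of the table (30% v 5%; power 96% at 62 per arm, 99% at 75). A new scar lying over an old one could still be missed.

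The cost is a few minutes of examination time and one case report form page, with no new visit or procedure. The reported rate will exclude old scars, which is what the outcome's name already implies.

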## 6.1.1. Inclusion Criteria:

- Women 18-89 years old
- Diagnosed with VIN II/III (diagnosed by pathology)
- Referred for vulva sparing treatment for dysplasia
- Available for follow-up of treatment for 12 months

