## 14. Statistical Analysis

A per protocol analysis will be conducted. Participants receiving treatment per protocol will be included in the final analysis. Investigators will not have the option to change treatment assignment.

Descriptive statistics using means, frequencies, and percentages will be computed to describe the study population. Participant data will be analyzed employing the per protocol approach. Student's *t*-test (for continuous variables) and chi-square tests (for categorical variables) will be used to compare the two groups for demographic, and secondary outcome variables: pain, scarring, QOL scores. For the primary outcome measure rate of recurrence for each of the study endpoints, 3 months, 6 months and 12 months will be calculated per treatment arm and compared with initial bivariate analysis using chi-square analysis. Additional predictors for recurrence (pain, scarring, sexual function, and general wellness) will be compared similarly with chi-square for categorical variables and t-tests for continuous variables. Potential covariates (age, race, previous disease, etc.) will also be analyzed using bi-variate analysis. Variables found to be significant in the bivariate analysis will be included in multivariable analysis using logistic regression. Logistic regression models will be used to identify significant independent predictors associated with recurrence for each treatment arm. The logistic model will allow for control of study covariates. A p-value of <0.05 will be used to demonstrate statistical significance. IBM SPSS version 22 will be used for all statistical analyses.

Incidence of AEs and SAEs will be compared between treatment arms using chisquare analysis. A p-value of <0.05 will be used to demonstrate statistical significance.

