# Appendix 1.3 Female Sexual Function Index (FSFI)

These questions ask about your sexual feelings and responses during the past 4 weeks. Please answer the following questions as honestly and clearly as possible.

Sexual activity can include caressing, foreplay, masturbation and vaginal intercourse. Sexual intercourse is defined as penile penetration (entry) of the vagina. Sexual stimulation includes situations like foreplay with a partner, self-stimulation (masturbation), or sexual fantasy.

Sexual desire or interest is a feeling that includes wanting to have a sexual experience, feeling receptive to a partner's sexual initiation, and thinking or fantasizing about having sex.

Sexual arousal is a feeling that includes both physical and mental aspects of sexual excitement. It may include feelings of warmth or tingling in the genitals, lubrication (wetness), or muscle contractions.

1. Over the past 4 weeks, how often did you feel sexual desire or interest?

- Almost always or always
- Most times (more than half the time)
- Sometimes (about half the time)
- A few times (less than half the time)
- Almost never or never

2. Over the past 4 weeks, how would you rate your level (degree) of sexual desire

or interest?

- o Very high
- o High
- o Moderate
- o Low
- Very low or none at all

3. Over the past 4 weeks, how often did you feel sexually aroused ("turned on") during sexual activity or intercourse?

- No sexual activity
- Almost always or always
- Most times (more than half the time)
- Sometimes (about half the time)
- A few times (less than half the time)
- Almost never or never

4. Over the past 4 weeks, how would you rate your level of sexual arousal ("turn on") during sexual activity or intercourse?

- No sexual activity
- Very high
- o High
- o Moderate
- o Low
- Very low or none at all

5. Over the past 4 weeks, how confident were you about becoming sexually aroused during sexual activity or intercourse?

- No sexual activity
- Very high confidence
- High confidence
- Moderate confidence
- Low confidence
- Very low or no confidence

6. Over the past 4 weeks, how often have you been satisfied with your arousal (excitement) during sexual activity or intercourse?

- No sexual activity
- Almost always or always
- Most times (more than half the time)
- Sometimes (about half the time)
- A few times (less than half the time)
- Almost never or never

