- Very dissatisfied

16. Over the past 4 weeks, how satisfied have you been with your overall sexual life?

- Very satisfied
- Moderately satisfied
- o About equally satisfied and dissatisfied
- Moderately dissatisfied
- Very dissatisfied

17. Over the past 4 weeks, how often did you experience discomfort or pain during vaginal penetration?

- Did not attempt intercourse
- Almost always or always
- Most times (more than half the time)
- Sometimes (about half the time)
- A few times (less than half the time)
- o Almost never or never

18. Over the past 4 weeks, how often did you experience discomfort or pain following vaginal penetration?

- Did not attempt intercourse
- Almost always or always
- Most times (more than half the time)
- Sometimes (about half the time)
- A few times (less than half the time)
- Almost never or never

19. Over the past 4 weeks, how would you rate your level (degree) of discomfort or pain during or following vaginal penetration?

- Did not attempt intercourse
- o Very high
- o High
- o Moderate
- o Low
- Very low or none at all

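### FSFI means and dysfunction rates are compared unadjusted between arms regardless of sexual activity, so women inactive before treatment dilute the comparison

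*Combined protocol and SAP*

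**What the plan says.** Section 4 (Secondary outcomes) names two instruments for sexual function: "The Female Sexual Function (FSFI) and the Female Sexual Distraught Survey will be used to examine sexual function at each time point". It plans a within-arm look at change, "Changes in sexual function will be compared to baseline within each treatment arm", and a between-arm look at levels, "Overall sexual dysfunction rates will be compared between treatment arms for each study time interval". Section 14.2 adds that mean scores for "function and distraught will be determined for each treatment arm per study time-point". Section 14 supplies the tests: the t-test and chi-square "will be used to compare the two groups for demographic, and secondary outcome variables: pain, scarring, QOL scores". I read the sexual-function surveys as belonging to that last group. The logistic model in section 14 is for recurrence only.

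The age criterion in section 6.1.1 is "Women 18-89 years old". Neither 6.1.1 nor 6.1.2 mentions sexual activity.

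In the FSFI printed in Appendix 1.3, items 3 to 14 each offer "No sexual activity" and items 17 to 19 each offer "Did not attempt intercourse". Items 1, 2, 15 and 16 offer neither. The documents contain no FSFI coding, no rule for these answers, no dysfunction cut-off and no rule for skipped items, although section 10 lets women skip any question.

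**The concern.** Hypothesis 3 says that aspiration disturbs sexual and psychosocial function less than laser over 12 months. A woman who had no sexual activity before treatment, and has none afterwards, can show no treatment effect on most FSFI items. She is nevertheless in the comparison, and the outcome depends on a coding choice left until the data are in:

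- If her answers take the lowest value, she has a very low score and is likely to count as dysfunctional, in either arm, whatever the device did.
- If they are set to missing, she has no complete total and drops out of the mean.

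The first choice shrinks the difference between arms and widens the spread. The second changes the population without saying so. What is at stake is a real difference in sexual function being missed, or a result that depends on an unstated coding.

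**Working it through.** **Plan's own figure.** There is no sample-size statement for the FSFI. Section 6.2 gives 62 per arm for recurrence (37.5% v 15%, 80% power, alpha 0.05). The two-sided pooled formula gives 59, and 62 gives 82% power; this has no bearing here. I use 62 only as the number analysed. It is optimistic at 12 months, because women leave at recurrence.

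**Step 1: count.** Items 3–14 (12) plus items 17–19 (3) make 15 of 19, or 79%.

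**Step 2: mean scores, unadjusted.** Every score input is an assumption: raw item sum, no-activity and no-intercourse answers scored 0; active women mean 60, SD 12; inactive women mean 12, SD 3; true difference 6 points in active women and none in inactive women; activity status stable; a share k inactive in both arms; two-sided alpha 0.05.

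- Difference in all women = 6(1 − k)
- SD in all women = √[(1 − k)·12² + k·3² + k(1 − k)·(60 − 12)²]
- λ = difference / (SD·√(2/n)); power = Φ(λ − 1.96) + Φ(−λ − 1.96)

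For k = 20%, all women: variance = 115.2 + 1.8 + 368.64 = 485.64, so SD = 22.0; difference = 4.8; λ = 4.8 / (22.04 × 0.1796) = 1.21; power 23%. Active at V0: n = 62 × 0.8 = 49.6; λ = 6 / (12 × 0.2008) = 2.49; power 70%.

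| Inactive share k | SD, all women | Difference, all women | Power, all women | Power, active at V0 |
|---|---|---|---|---|
| 5% | 15.7 | 5.7 | 52% | 77% |
| 10% | 18.4 | 5.4 | 37% | 75% |
| 20% | 22.0 | 4.8 | 23% | 70% |
| 30% | 24.2 | 4.2 | 16% | 64% |
| 40% | 25.4 | 3.6 | 12% | 58% |

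**Step 3: dysfunction rates.** Assume that every inactive woman is classed as dysfunctional, that the rates in active women are 40% v 20%, and that all 75 per arm are analysed. The all-women rates are k + (1 − k)·0.40 and k + (1 − k)·0.20. At k = 30% they are 58% v 44%, and inactive women make up 0.30 / 0.51 = 59% of cases.

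| k | Power, all women | Power, active only | Inactive share of dysfunction cases |
|---|---|---|---|
| 10% | 63% | 72% | 27% |
| 20% | 51% | 67% | 45% |
| 30% | 40% | 61% | 59% |
| 50% | 25% | 47% | 77% |

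**Step 4: women who stop later.** Take k = 20% in step 2, and let 10% or 20% of the V0-active women in each arm become inactive and score as inactive women do. Their difference becomes 6 × 0.9 or 6 × 0.8, with n still 49.6, and power falls to 31% or 19%. In all women the inactive share becomes 1 − 0.8 × 0.9 = 28% or 1 − 0.8 × 0.8 = 36%, and power is 17% or 14%. The V0-active set still does better, but the scoring of follow-up answers matters a great deal.

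**The case against.** The strongest reply is that most of the loss in step 2 comes from ignoring baseline. Hypothesis 3 is about change. Suppose change scores were compared between arms in all women, with stable activity and a within-person correlation of 0.5. The change variance is then (1 − k)·144 + k·9 + k(1 − k)·18, where the last term averages over the arms the spread created by the 6-point effect. Power is 69%, 62% and 54% at k = 20%, 30% and 40%, close to the 70%, 64% and 58% above and with nobody excluded. At correlation 0.7 it is 88%, 82% and 75%.

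This stands, and the fix should include the V0 score. It does not rescue the plan as written, which examines change only within each arm. Nor does it make the V0-active set redundant. Adjusting that set for the V0 score at correlation 0.5 gives a residual SD of 12·√(1 − 0.25) = 10.4 and power of 82%, 77% and 70%. Its estimate is also the 6-point difference in women who can show one, not 6(1 − k).

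Other replies that stand:

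- Randomization balances prior inactivity in expectation. A chance imbalance is ordinary sampling error.
- The Female Sexual Distress Scale (FSDS-R) is already planned for all women, and none of its 13 items has a no-activity option.
- The introduction places the disease generally in the fourth and fifth decades, so the upper age limit of 89 says little about the inactive share.

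**Conclusion.** The point holds as one of dilution and an unspecified scoring rule in a secondary outcome. It does not touch the primary endpoint. Under the assumptions of step 2, unadjusted power in all women is 52% to 12% for inactive shares of 5% to 40%, against 77% to 58% in women active at V0. The direction was the same for means and for rates at every non-zero share tried; the size is conditional.

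Four stronger readings are tempting, and the documents do not support them:

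- That the 15 items cannot be answered without activity. Each prints an answer for that case; the answer is uninformative about function.
- That a woman without a partner is scored as dysfunctional. Appendix 1.3 counts masturbation as sexual activity, so she may be able to rate items 3 to 13. Items 17 to 19 depend on attempted intercourse, which is a separate condition.
- That the endpoint largely measures who is sexually active. The inactive share and the coding are not given. In step 3 inactive women exceed half of the dysfunction cases only from roughly 25% to 30% inactive.
- That the comparison is systematically biased between arms by prior inactivity. The main harm is lost power and a shrunken difference.

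**What to change.** In sections 4 and 14.2:

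1. Make the between-arm FSFI comparison in women who report sexual activity on the V0 FSFI, adjusted for the V0 score. Section 8 and the study calendar place the surveys at V0 and randomization at V1, so this subset is defined before randomization. The per-protocol rule (sections 9 and 14) and exit at recurrence (section 4) still select the women analysed at 6 and 12 months, so it should not be described as a fully randomized comparison.
2. Report by arm, as a separate outcome, the proportion of these women still sexually active at 6 and 12 months, since stopping may itself be harm. Before analysis, state how no-activity and no-intercourse answers at follow-up are scored and how dysfunction is defined, and add a sensitivity analysis under the other coding.
3. Keep the planned FSDS-R as the sexual outcome for all women, and show the all-women FSFI, adjusted for the V0 score, as supportive.

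The cost is analysis wording; every item is already collected. The price is an FSFI result that applies to women active at baseline and uses fewer of them. Women who were inactive at V0 and resumed activity would appear only in the supportive analysis and the FSDS-R.
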